A Multi-center Clinical Study on the Efficacy and Safety of Kuntai Capsule Alone and in Combination With Hormones in the Treatment of Early-onset Hypoovarian Function

NCT05021094

Date: August 4, 2021

Research Proposal Summary

| Scheme number | HYKT18017S |
|------------------------|---|
| Scheme name | A Multi-center Clinical Study on the Efficacy and Safety of Kuntai Capsule Alone and in |
| | Combination With Hormones in the Treatment of Early-onset Hypoovarian Function |
| Version number/date | Version 2.1 , June 18 , 2021 |
| sponsor | Shanghai Haitian Pharmaceutical Technology Development Co., Ltd. |
| Clinical trial staging | Post-marketing clinical re-evaluation |
| test drug | Heyan Kuntai Capsules [®] (Z20000083), each0.5g, was produced by Guiyang Xintian Pharmaceutical Co., Ltd. |
| Indications | POI (including subclinical stage) |
| Test purposes | To evaluate [®] the efficacy and safety of Heyan Kuntai Capsules alone or in combination with hormone therapy in patients with POI (including subclinical stage) in improving ovarian function . |
| Research design | Prospective, multicenter, randomized, controlled clinical trial design |
| total number | It is planned to complete 120 cases (considering the 20% dropout rate, at least 150 cases need to be |
| of cases | enrolled) |
| number of research | 6_ |

| centers | |
|--------------|---|
| Study period | 24 months |
| research | Diagnostic criteria : |
| object | The diagnostic criteria for premature ovarian insufficiency (POI) refer to the "2017 Chinese |
| | Expert Consensus on Clinical Diagnosis and Treatment of Premature Ovarian Insufficiency" and |
| | "2016 Expert Consensus on Hormone Supplementation Therapy for Premature Ovarian |
| | Insufficiency"; including: (1) Age <40 years old; (2) oligomenorrhea or amenorrhea for at least 4 |
| | months; (3) at least 2 times serum basal follicle-stimulating hormone (FSH) > 25 IU/L (interval > 4 |
| | weeks). Subclinical POI: FSH level is 15~25 IU/L, which is a high-risk group. |
| | The diagnostic criteria for premature ovarian failure (POF) refer to the "2017 Chinese Expert |
| | Consensus on Clinical Diagnosis and Treatment of Premature Ovarian Insufficiency", which refers |
| | to amenorrhea, FSH>40IU/L, and decreased estrogen levels before the age of 40, accompanied by |
| | varying degrees of perimenopause Stage symptoms are the terminal stage of POI. |
| | standard constrain: |
| | 1. 18 years old ≤ age < 40 years old; |

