| | 2. At least two (>4 weeks interval) basal FSH≥15IU/L, with or without oligomenorrhea or |
| | menopause. |
| | 3. Informed consent, voluntary experiment. |
| | Exclusion criteria: |
| | 1. pregnant and lactating patients; |
| | 2. Patients with endometriosis , adenomyosis , endometrial lesions (submucosal fibroids , |
| | endometrial polyps, etc.), uterine fibroids >4cm or hysterectomy; |
| | 3. Patients with known or suspected history of breast cancer and estrogen-dependent |
| | malignancies; |
| | 4. a personal history of venous thromboembolism (VTE) or with a high risk of VTE (including |
| | body mass index > 30 kg/m ² , smoking, family history of thrombophilia); |
| | 5. Porphyria patients; |
| | 6. Patients with serious primary diseases such as cardiovascular, liver, kidney, hematopoietic |
| | system or mental illness; |

- 7. Patients who are participating in other clinical trials or have participated in other clinical trials within the past three months;
- 8. Patients with suspected or real history of alcohol and drug abuse;
- 9. Known allergy to the investigational drug or its components;
- 10. Other patients deemed unsuitable for participation in this trial by the investigator.

Note: Patients who were receiving hormone replacement therapy at the time of recruitment were required to take at least a 3 -month suspension of medication to participate in this trial.

Trial grouping

and medication

1 POI patient

According to the random sequence generated by computer, eligible patients were randomly assigned to Kuntai group, control group and combination group according to 1:1:1.

- (A) Kuntai group (30 cases): Oral Kuntai capsules, 4 capsules at a time, 3 times a day, 28 days as a course of treatment, taking medicine for 3 courses;
- (B) Control group (30 cases): the sequential regimen of estrogen and progesterone was used, and the drug was estradiol tablets/estradiol dydrogesterone tablets (fenmetone), and red tablets (estradiol, 2 mg/d), and gray tablets (estradiol, 2 mg/d, dydrogesterone, 10 mg/d) were taken for the next 14 days, 28 days as a course of treatment, and three courses of medication were taken.
- (C) Combination group (30 cases): On the basis of hormone therapy, Kuntai Capsules were added, and the dose was the same as that of Kuntai group and hormone group for 3 months.

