- 2. Patients with POI in subclinical stage: self-control before and after experiment group (30 cases): Oral Kuntai capsules, 4 capsules at a time, 3 times a day, 28 days as a course of treatment, taking medicine for 3 courses of treatment.

Treatment and

follow-up

- 1. Course of treatment: 28 days as a course of treatment, taking medicine for 3 courses of treatment
- 2. Visit points: before treatment (stage V $_{0}$, screening period, days -35 $\rm to~0$), baseline period (day
- 0), after 3 months of treatment (stage V_1 , days 84 to 105), drug withdrawal 3 months later (V_2 stage, 168-210 days) and 6 months after drug withdrawal (V_3 stage, 252-315 days).

Specific inspection items include:

- 1. The patient 's hormone levels (basal FSH, LH, E₂) were detected in V₀, V₁, and V₂ stages;
- 2 Anti-Müllerian hormone (AMH) was detected in patients at V 0 and V 1 stages;
- 3 The patients underwent B-ultrasound at V 0 and V 1 stage to monitor the follicular development,

| | record the number of antral follicles (AFC), ovarian hemodynamic parameters (PSV, EDV, S/D, RI |
|----------------|---|
| | and PI); |
| | 4. Modified Kupperman score was performed in V $_{0}$, V $_{1}$ and V $_{2}$ stage; |
| | 5 Pregnancy was recorded at the V $_2$ outpatient follow-up for patients with reproductive needs; |
| | 6 patients at V $_{0}$ and V $_{1}$ to detect blood routine (RBC, WBC, PLT, HGB) , liver function (ALT, |
| | AST) and renal function (BUN, Cr), and recorded adverse events. |
| | |
| | Note: |
| | 1 Basal follicle-stimulating hormone (FSH) \geq 15IU/L at first visit in patient V0, and if other |
| | inclusion criteria are met, if the patient has a history of testing with a baseline FSH ≥ 15 IU/L in |
| | the past (interval> 4 weeks), he or she can be included in this study and drug therapy can be |
| | started; (Interval > 4 weeks) If the basic FSH \geq 15 IU/L has not been diagnosed, the patient is |
| | required to visit the hospital again after 4 weeks. If the basic FSH is still \geq 15 IU/L, they can be |
| | included in this study and drug therapy can be started. |
| | 2 For patients with regular menstrual periods, the basal FSH and antral follicle count (AFC) |
| | should be followed up on the 2nd to 4th day of the menstrual cycle. If the patient has menstrual |
| | cramps after the follow-up and has not exceeded the visit window, they are required to re-examine |
| | on the 2nd to 4th day of the menstrual cycle and record the examination data. |

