A Multi-center Clinical Study on the Efficacy and Safety of Kuntai Capsule Alone and in Combination With Hormones in the Treatment of Early-onset Hypoovarian Function

NCT05021094

Date : August 4 , 2021

Statistical analysis

The case observation form completed by the test center was reviewed and returned by the project team of Shanghai Haitian Pharmaceutical Technology Development Co., Ltd., and the data was processed by a statistical analyst. The data in the case report form is entered in two copies, and the database is locked after verification and confirmation. SPSS26.0 software was used for statistical analysis. The full analysis set (FAS) and the per-protocol set (PPS) were used for effectiveness analysis, and the safety data set (SS) was used for safety analysis. Measurement data were expressed as mean \pm standard deviation ($\bar{x} \pm s$), multiple time points were compared by repeated measures analysis of variance, and pairwise comparisons were by Bonferroni test; enumeration data were expressed by the number of cases or percentages, and χ^2 was used.Test for statistical comparison.P<0.05 indicated that the difference was statistically significant.

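### Six centres, but no centre strata in the described allocation and no centre term in the SAP: avoidable imbalance and noise if centres differ

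*Protocol*

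**What the plan says.** The Research design row of the protocol summary reads "Prospective, multicenter, randomized, controlled clinical trial design", and the row for research centres gives six. The total is given as "It is planned to complete 120 cases (considering the 20% dropout rate, at least 150 cases need to be" enrolled).

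Under Trial grouping and medication, POI patients are allocated thus: "According to the random sequence generated by computer, eligible patients were randomly assigned" to "Kuntai group, control group and combination group according to 1:1:1", with 30 cases in each. No stratum, block or minimisation factor is named. The subclinical patients form a separate "self-control before and after experiment group (30 cases") and are not randomised.

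The co-primary endpoints are FSH and the modified Kupperman score, both taken at V0, V1 and V2. Secondary endpoints include LH, E2, AMH, antral follicle count and Doppler parameters. The protocol does not say where hormones are assayed, who reads the scans or who scores the Kupperman scale.

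The SAP is one paragraph. For continuous data, "multiple time points were compared by repeated measures analysis of variance", followed by Bonferroni pairwise tests. Counts are compared by chi-square. No centre term or other covariate appears.

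**The concern.** Hormone values, follicle counts, Doppler indices and interviewed symptom scores can all vary between hospitals, through case mix, assay platform, equipment or rater. The documents describe nothing that would limit this variation.

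Two things follow when centre enters neither the allocation nor the model. Arms can be uneven within a centre by chance, so part of a between-arm difference may reflect which centre the women came from. Between-centre variance also stays in the error term of any contrast that does not remove it by differencing. With 30 women per arm there is little precision to spare, and both effects can be prevented at almost no cost.

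**Working it through.** **Inputs from the documents.** Six centres; three randomised arms of 30 completers; 30 non-randomised subclinical patients; 20% dropout; significance level 0.05.

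**Assumptions.** Two-sided tests, equal centres, an effect of 0.7 SD, and a centre share of outcome variance (ICC) of 0.05, 0.10 or 0.20. The documents give no effect size, SD, power or ICC.

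**The plan's own figure.** 3 × 30 + 30 = 120 completers, and 120 / (1 − 0.20) = 150, as stated. The randomised part is 3 × 30 = 90, or 90 / 6 = 15 per centre and 5 per arm per centre.

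**Imbalance within a centre.** With arm totals fixed at 30, the chance that a centre of 15 splits as (a, b, c) is C(30,a)·C(30,b)·C(30,c) / C(90,15). Summing over all splits whose largest and smallest arms differ by 4 or more gives 0.44. Under simple randomisation the probability is 15!/(a! b! c!) / 3^15, and the sum is 0.50. By simulation, at least one centre has 2 or fewer women in some arm in about 68% of trials with fixed totals, and in about 80% under simple randomisation.

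**What the imbalance does to an arm difference.** With fixed totals, the variance of (n_A − n_B) in one centre is 15 × (2/3) × (75/89) = 8.43. Over six centres, the centre contribution to the difference in means has SD √(ICC × 6 × 8.43 / 30²) = √(ICC × 0.0562). That is 0.053, 0.075 and 0.106 total-SD units at ICC 0.05, 0.10 and 0.20. The standard error of the contrast is √(2/30) = 0.258.

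**Power for a single-time-point contrast.** Ignoring centre: 0.7 / 0.258 = 2.711, and Φ(2.711 − 1.96) = 0.774. Balancing on centre and fitting it reduces the residual SD to √(1 − ICC):

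| ICC | 2.711 / √(1 − ICC) | Power by formula | Simulated, strata plus term |
|---|---|---|---|
| 0.05 | 2.782 | 0.794 | 0.787 |
| 0.10 | 2.858 | 0.815 | 0.806 |
| 0.20 | 3.031 | 0.858 | 0.851 |

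The simulation used 6,000 trials per setting; the unstratified design without a centre term gave 0.77 throughout. At ICC 0, strata plus term cost about 1 point or less.

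The SAP's Bonferroni step lowers the absolute values but leaves a gain. At 0.05/3 and an assumed 0.723 SD (the difference that gives 80% power at 0.05), the formula gives 0.658 ignoring centre and 0.684, 0.711 and 0.769 after removing centre variance.

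**Why both changes belong together.** With strata but no centre term, the standard error still contains centre variance that the design has removed. Simulated type I error at ICC 0.20 is then about 0.03 (0.031 to 0.036 over separate runs). With the term but no strata there is no gain at ICC 0.05 or below.

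**Change from baseline.** If a centre adds the same constant at every visit, the constant cancels in the difference. Simulated power at ICC 0.05, 0.10 and 0.20 (0.7 SD of change) was 0.77, 0.76 and 0.76 without strata or term, and 0.76, 0.78 and 0.77 with both. These differences are within simulation error.

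**The case against.** The strongest objection is that the planned analysis is over time. If the group-by-time contrast carries the treatment effect, a stable additive offset from assay, scanner or rater drops out and the fix buys nothing. This stands, and it rules out saying that every contrast loses power. It does not dispose of the point. Proportional assay differences and centre differences in change over time do not cancel, and the SAP does not say which contrast of the ANOVA is primary.

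A reader might infer that each centre uses its own hormone tests, scanners and interviewers. The documents do not say so. On-site scanning and symptom scoring are reasonable guesses, but a central hormone laboratory is not excluded. All that can be said is that no central or standardised arrangement is described.

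A reader might also take the silence on strata as proof that one unstratified list was used. The protocol text is a summary, so it supports only the statement that no centre strata are named.

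Finally, the gain at ICC 0.05 is only 1 to 2 points, and both the ICC and the effect size are assumed. That is true, and it limits the importance of the point.

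**Conclusion.** The point holds as a cheap improvement in precision and balance for the three randomised POI arms. Arm balance is not at issue in the subclinical before-after group.

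If centres differ in level, the fix is worth about 2, 4 or 8 points of power on a single-time-point contrast at ICC 0.05, 0.10 or 0.20, assuming 0.7 SD, 30 per arm and equal centres. It is worth nothing for change from baseline under stable additive offsets. About 44% of centres would have an arm gap of 4 or more with fixed arm totals (50% under simple randomisation).

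A reader might infer bias or false-positive findings. Neither follows: the imbalance is random, and simulated type I error without strata or a centre term stays near 0.05.

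**What to change.** - **Allocation.** Stratify the POI sequence by centre, with central concealed allocation in permuted blocks of varying size (for example 3 and 6). If centre strata are already in use, say so in the protocol.
- **Analysis.** Add centre, as a six-level fixed factor or a random effect, to the models for FSH, the Kupperman score and the continuous secondary endpoints. Make this change together with the stratification.
- **Measurement.** Keep all of a woman's on-study hormone tests in one laboratory. State whether assays, scan readings and Kupperman scoring are central or standardised.

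The cost is a regenerated list, one model term and a sentence on laboratories. The downsides are 5 degrees of freedom for a fixed factor (6 − 1), incomplete last blocks in each centre, and a loss of about 1 point of power or less if centres do not differ.

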| study endpoint | Primary endpoint : FSH, modified Kupperman score |
| | Secondary endpoints : |
| | (1) FSH/LH, LH, E ₂ ; (2) Antral follicle count (AFC); (3) Anti- Müllerian hormone (AMH); (4) |
| | Proportion of patients with normal menstruation; (5) Ovarian hemodynamics parameters (PSV, |
| | EDV, S/D, RI and PI); (6) Clinical pregnancy rate (patients with reproductive needs). |
| security | 1 Blood routine (RBC, WBC, PLT, HGB), liver function (ALT, AST) and renal function (BUN, |
| indicators | Cr); |
| | 2 Patient adverse events were recorded. |

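### Conception is a wanted outcome, but pregnancy is recorded only at V2 and only for some women, and no rule covers hormone values taken in pregnancy

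*Protocol*

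**What the plan says.** **Endpoints.** The Protocol's study endpoint section gives "Primary endpoint : FSH, modified Kupperman score". LH, FSH/LH and E2 are secondary, as is "Clinical pregnancy rate (patients with reproductive needs".

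**Sampling.** Item 1 of the specific inspection items states "hormone levels (basal FSH, LH, E₂) were detected in V₀, V₁, and V₂ stages". AMH and AFC are taken at V0 and V1. V1 falls "after 3 months of treatment (stage V_1 , days 84 to 105", and V2 falls three months after drug withdrawal ("stage, 168-210 days").

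**Pregnancy.** Apart from the endpoint, pregnancy appears twice. Women who are pregnant at entry are excluded ("pregnant and lactating patients"), and item 5 reads "5 Pregnancy was recorded at the V $_2$ outpatient follow-up for patients with reproductive needs". No pregnancy record is listed at V1, and none at V2 for women without reproductive needs. The documents contain no contraception requirement.

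**Sampling day.** Note 2 ties basal FSH and AFC to cycle days 2–4, but only for women whose periods are regular.

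**Analysis.** The SAP says "multiple time points were compared by repeated measures analysis of variance". It names a full analysis set and a per-protocol set without defining either, and has no rule for missing values or for events such as conception.

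**The concern.** In pregnancy, FSH and LH are suppressed and E2 is raised, so the values no longer describe basal ovarian function. This is general physiology, not a figure from the documents. The plan expects some conceptions but does not say how such a woman's hormone values are treated.

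Two routes are open. If her sample is taken and kept, the primary FSH mean falls and pregnancy is credited as a hormonal improvement. If she is not sampled, a classical repeated measures ANOVA works on complete cases, so by default her V0 and other values go too, and a woman with a good ovarian outcome leaves the analysis. The choice between routes would be made without a prior rule, possibly after the data are seen. If arms differ in conceptions, the effect would not cancel between them.

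The recording rule adds to this. A pregnancy present at V1, or one in a woman without stated reproductive needs, need not be recorded anywhere, so the affected hormone value could not be recognised afterwards.

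**Working it through.** **1. The plan's own figures.** Four groups of 30 give 4 × 30 = 120 completers, and 120 / (1 − 0.20) = 150 enrolled, as stated. The documents give no FSH or E2 mean or SD, no effect size and no conception rate. Everything below except step 2 therefore rests on stated assumptions, with n = 30 per arm.

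**2. What the V2 record can tell.** The V1 and V2 samples lie between 168 − 105 = 63 and 210 − 84 = 126 days apart. Without a conception date, a pregnancy noted at V2 cannot be placed before or after the V1 sample.

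**3. Who is exposed.** A pregnant woman cannot give a cycle day 2–4 sample, so Note 2 largely protects women with regular periods. The Protocol's diagnostic criteria for POI require oligomenorrhea or amenorrhea, although the inclusion criterion admits women with or without it. The randomised POI stratum is thus where Note 2 is likely to protect least.

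**4. Route A: the value is counted.** With k conceptions at FSH f in an arm whose mean is otherwise μ, the mean falls by k(μ − f)/30. Assumed: μ = 20 to 60 IU/L, f = 0 to 1 IU/L, SD = 30% to 50% of μ.

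| μ | f | Fall, k = 1 | Fall, k = 3 | In SD, k = 1 | In SD, k = 3 |
|---|---|---|---|---|---|
| 20 | 1 | 19/30 = 0.63 | 1.90 | 0.06–0.11 | 0.19–0.32 |
| 20 | 0 | 20/30 = 0.67 | 2.00 | 0.07–0.11 | 0.20–0.33 |
| 60 | 1 | 59/30 = 1.97 | 5.90 | 0.07–0.11 | 0.20–0.33 |
| 60 | 0 | 60/30 = 2.00 | 6.00 | 0.07–0.11 | 0.20–0.33 |

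The subclinical group may have a narrower spread. If FSH were even over its defining range of 15–25 IU/L, the SD would be 10/√12 = 2.9. At μ = 20, one conception would then be 0.22–0.23 SD and three 0.66–0.69 SD. That group has no concurrent control.

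**5. Route B: the woman is removed.** If k women would otherwise have had FSH lower than the rest by d, removing them raises the mean by kd/30. For d = 5 to 20 IU/L this is 0.17 to 0.67 IU/L for k = 1 and 0.5 to 2.0 IU/L for k = 3. The direction is opposite to Route A.

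**6. Scale.** The difference detectable with 80% power at 30 per arm, two-sided 0.05, is (1.960 + 0.842) × √(2/30) = 0.72 SD. With Bonferroni for three pairs it is 0.84 SD.

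**7. E2.** Assume a non-pregnant mean of 30 pg/mL (SD 15) and a pregnancy value E. One conception raises the arm mean by (E − 30)/30. For E = 1,000 this is 32.3 pg/mL (2.2 SD), for half that value 15.7 (1.0 SD), and for a tenth of it 2.3 (0.16 SD). The size depends almost entirely on E.

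**The case against.** The strongest reply is that the plan has more protection than it first appears, and that the primary effect is small.

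- **A reader might infer that pregnancy is not checked at all at follow-up.** That is true of V1 only. At V2 it is recorded for women with reproductive needs, who are probably those most likely to conceive. What stands is that this is an outcome record, not linked to the hormone sample or to any handling rule. The V1 ultrasound for follicles is not a pregnancy test and could miss a very early conception.
- **Note 2 counts.** For women with regular periods, keeping a value drawn in pregnancy as basal would depart from the plan. Women with oligomenorrhea or amenorrhea are not covered.
- **A reader might infer that the SAP prescribes complete-case deletion.** It does not. Deletion is the usual default of the named method, and imputation would be a third unspecified route. The gap is partly one instance of a SAP that defines neither its analysis sets nor its handling of missing data.
- **The Protocol text is headed as a summary.** The supportable claim is that these documents state no rule.

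**Conclusion.** The point holds as a gap in recording and analysis that should be closed, not as a threat to the trial as a whole. The recording rule would leave pregnancies at V1 and in women without reproductive needs uncaptured, and the named analysis has no stated way to handle them.

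For primary FSH the effect of one conception is small: about 0.06–0.11 SD if counted, against a detectable difference of 0.72 SD or more. Three conceptions in one arm would shift it by 0.19–0.33 SD, enough to matter if they fall unevenly. These ranges rest on the assumed pregnancy FSH, arm means and SDs; a narrower spread, as is possible in the subclinical group, makes the standardised shift larger. E2, a secondary endpoint, would be distorted more, by an amount set by the assumed pregnancy value.

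A reader might infer that the FSH comparison can no longer measure ovarian function. The documents do not support that: they give no conception rate, and the shifts per conception are modest.

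**What to change.** 1. Record pregnancy status for every woman at V1 and V2 alongside the hormone sample, with the estimated conception date if she is pregnant.
2. State in the SAP that FSH, LH, FSH/LH, E2, AMH and AFC values taken in pregnancy are not counted as basal ovarian values.
3. Analyse FSH with a mixed model for repeated measures, so that a missing visit does not remove the woman's other visits.
4. Add a sensitivity analysis of FSH that ranks pregnancy as the best outcome. Setting values to missing still leaves women with a good ovarian outcome out of that visit's mean, and the mixed model does not remove bias if conception depends on the unobserved FSH.

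Cost: one added case report form field, a simple pregnancy check where status is unclear, a few hormone values set to missing, and a change from the model the SAP names. Sample size and treatment are unaffected. The field has to be in place while visits are running, since conception dates may not be recoverable later.

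### The normal-menstruation endpoint ignores menstrual status at entry although regularly menstruating women are eligible; it should be analysed by V0 status

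*Protocol*

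**What the plan says.** The protocol's study endpoint section lists "Proportion of patients with normal menstruation" as secondary endpoint (4). It gives no definition of normal, no time point, no baseline condition and no restricted denominator. The same list does restrict another item: "Clinical pregnancy rate (patients with reproductive needs").

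On entry, inclusion item 2 asks for "At least two (>4 weeks interval) basal FSH≥15IU/L, with or without oligomenorrhea or" menopause. Note 2 under treatment and follow-up sets a sampling rule that begins "For patients with regular menstrual periods, the basal FSH and antral follicle count (AFC"), so the plan expects some women with regular cycles.

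The diagnostic criteria separate two groups. POI includes, as its second element, "2) oligomenorrhea or amenorrhea for at least 4" months. The other group is described as "Subclinical POI: FSH level is 15~25 IU/L, which is a high-risk group", without a menstrual element. The 1:1:1 randomisation to Kuntai, control and combination (30 each) stands under the heading for POI patients. The subclinical patients form one group of 30, compared with their own baseline.

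The SAP adds only that "enumeration data were expressed by the number of cases or percentages", with a chi-square test at P<0.05. It mentions no stratification or adjustment for baseline status.

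**The concern.** A woman who menstruates normally before her first dose has nothing to restore, yet she adds to the numerator of endpoint (4) if she simply stays as she was. The percentage therefore mixes two quantities: restoration among women who were abnormal at V0, and maintenance among women who were normal.

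In the subclinical cohort this sets a floor under the post-treatment figure and a ceiling on improvement. With no comparator arm, a high percentage could be read as treatment benefit when it describes who was enrolled. In the randomised arms, any women regular at entry would shrink the difference between arms and reduce the chance of detecting a real effect on restoration.

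**Working it through.** **The plan's own figure.** 4 groups × 30 = 120 completers, and 120 / (1 − 0.20) = 150, which matches the stated enrolment. The plan gives no rate, effect size or power for any endpoint, so every rate below is an assumption. Sidedness is not stated and is taken as two-sided. Power is for one pairwise comparison at 0.05.

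**Who can be regular at entry.**

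| Rule | Menstrual requirement |
|---|---|
| Inclusion item 2 | none |
| Subclinical definition (FSH 15–25 IU/L) | none |
| POI diagnosis (heading of the randomised part) | oligomenorrhea or amenorrhea for at least 4 months |

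Regular women plainly belong in the subclinical cohort. For the randomised arms, item 2 and the POI diagnosis give different answers, and the text does not say which one governs. Nor does it say where a regularly menstruating woman with FSH above 25 IU/L goes: she meets item 2 but fits neither group definition.

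**Subclinical cohort.** Let b be the share regular at V0 and m the share of them who stay regular. With no recovery at all, the endpoint reads b × m.
- b = 0.5, m = 0.9: 0.5 × 0.9 = 45%.
- b = 0.7, m = 1: 70%, and only 30 × (1 − 0.7) = 9 women can show recovery.

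**Randomised arms, if some women are regular at entry.** Let f be the share regular at V0, m the maintenance rate and r the recovery rate among the others. Each arm's proportion is f·m + (1 − f)·r. If m is equal in the arms, the difference is (1 − f)(r₂ − r₁). With f = 0.3, m = 0.9 and recovery 10% v 40%:
- arm 1: 0.27 + 0.7 × 0.10 = 0.34
- arm 2: 0.27 + 0.7 × 0.40 = 0.55
- difference: 21 points instead of 30.

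Power was found by simulating trials with 30 women per arm. The number regular at V0 in each arm was binomial, and a chi-square test was applied. With recovery 10% v 40% and maintenance 90% in both arms:

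| Regular at V0 | All patients | Only women abnormal at V0 |
|---|---|---|
| 0% | 80% | 80% |
| 10% | 62% | 76% |
| 20% | 48% | 70% |
| 30% | 38% | 64% |

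Next, a Cochran-Mantel-Haenszel test stratified by V0 status was added, with 30% regular at V0:

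| Recovery | Maintenance | All patients | Abnormal at V0 only | Stratified |
|---|---|---|---|---|
| 10% v 40% | 90% v 90% | 38% | 64% | 55% |
| 20% v 50% | 60% v 90% | 66% | 54% | 72% |

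Restricting to women abnormal at V0 is best when treatment only restores cycles, and worst when it also preserves them. The stratified test beat the all-patient test in every scenario run with regular women at entry. With equal rates in both arms, the all-patient and restricted tests had type I error between 0.039 and 0.054, and the stratified test about 5%.

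**Why recovery alone misleads without a control.** Suppose 15 of 30 subclinical women are regular at V0 and 20% switch each way by chance. After treatment, 15 − 3 + 3 = 15 are regular, so there is no net change. Recovery among women abnormal at V0 is nevertheless 3/15 = 20%.

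**The case against.** The strongest reply concerns the randomised arms. The only between-arm comparison is under the POI heading, and POI as defined requires a menstrual disturbance. Item 2 uses the FSH threshold that covers both groups, so its menstrual waiver can be read as serving the subclinical women. Note 2 covers regular women anywhere in the trial and does not show that any are randomised. This stands. A reader might infer that the arm comparison is diluted as planned, but the documents do not establish it. They only leave it possible. A reader might also infer bias towards one arm, but under randomisation the mixing costs power and does not favour an arm.

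Second, the subclinical cohort is compared with its own baseline, so a woman who is normal at both times adds nothing to the change. This stands for a before-after comparison. However, endpoint (4) as written asks for no V0 proportion and no change, and even a before-after reading keeps the ceiling: women regular at V0 cannot show recovery.

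Third, the power loss depends on assuming that treatment does not affect maintenance. This also stands. When treatment preserves cycles, the all-patient analysis outperforms restriction to women abnormal at V0 (66% v 54%). That argues against restriction, but not against stratification.

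**Conclusion.** The point holds in a limited form. Endpoint (4) takes no account of menstrual status at V0, although regularly menstruating women are eligible. In the subclinical cohort its post-treatment value is partly a description of entry status, by an amount equal to the share regular at V0 times the share who stay so. In the randomised arms the consequence is conditional. If the POI diagnosis is enforced, no randomised woman is regular at entry and nothing is lost. If item 2 alone governs, power falls, for example from 80% to 38% with 30% regular at V0 on the first set of assumed rates.

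The tempting remedy of counting only recovery among women abnormal at V0 is not supported as a general rule. It loses power if treatment preserves cycles, and in an uncontrolled cohort it counts gains and ignores losses. All recovery, maintenance and baseline shares used here are assumptions. This is one secondary endpoint and does not touch the primary ones.

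**What to change.** 1. Reconcile inclusion item 2 with the POI diagnostic criteria, and state which governs entry to the randomised arms.
2. Define normal menstruation and the assessment visit, and classify each woman's menstrual status at V0 before treatment.
3. Randomised arms: compare arms on endpoint (4) with a test stratified by V0 status, such as Cochran-Mantel-Haenszel. Report restoration among women abnormal at V0 and maintenance among women normal at V0 separately.
4. Subclinical cohort: report the V0 proportion beside the post-treatment proportion, with the counts for both transitions (abnormal to normal and normal to abnormal). Do not use recovery among women abnormal at V0 alone as the analysis.

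Cost: a few sentences in the endpoint list and SAP, and a recorded V0 status. The listed inspection items do not name menstrual status, but applying the POI diagnosis and Note 2 already requires knowing it. The strata will be small, and one secondary endpoint needs a little more analysis. If no randomised woman is regular at V0, step 3 leaves that comparison essentially unchanged.
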